8.10 Study Schedule of Assessments

The study's schedule of events is shown in **Table 2**. Details of assessments are provided. Information captured in assessments will be documented in study- case report forms.

Table 2. Schedule of Assessments

Study Requirement	Screening	Study	Adverse events
Informed consent	X		
Medical history and medications	X		
Eligibility criteria assessment	X		
Reason(s) for extended ECG testing	X		
Symptoms during extended ECG testing		X	
Activities during extended ECG testing		X	

Adverse events related to ECG testing			X
Usability of ECG monitoring tests		X	
User preference of ECG monitoring tests		X	

8.11 Clinical Benefits/Risks

The HeartWatch is a non-invasive, accurate solution to ambulatory ECG monitoring.

8.11.1 HeartWatch Usage Benefit

The HeartWatch is painless and non-invasive. It is a small, light-weight, self-contained arm band that continuously records the electrical activity of the heart. It does not require electrodes (skin patches) or other bulky equipment and can be worn discreetly under everyday clothing.

The HeartWatch automatically detects and records abnormal heart rhythms and allows users to indicate when they are having symptoms, so that their physician can determine whether these symptoms are related to changes in the user's heart rhythm.

8.11.2 HeartWatch Usage Risks

While the HeartWatch is painless and non-invasive, participants may experience minor skin irritation from where it is in contact with their skin.

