Figure 4: Securing Disposable Strap onto Length Adjustment Lock.

8) Check for signs of loss in circulation in the subject's left arm. If loss in circulation is detected, repeat step 7. If the issue persists, consider starting again from step 3 with a larger strap size.

Note: Loss in circulation can present through the subject feeling numbness, tingling, cold hands, change in skin color, pain, fatigue, or swelling.

9) Push down the Back Hinge (see Figure 4) of the Length Adjuster Lock. This secures the strap in place.

10) Pull the Finger Loop (see Figure 5) to open the Quick Release in the Sensor Strap and loosen the strap. This allows for the sensors under the Main Enclosure to be shifted into position. The Main Enclosure sensors typically go on the anterior region of the bicep.

[figure not shown]

Figure 5: Sensor Strap with Quick Release open

11) Close the Quick Release by connecting the Magnet Pocket (see Figure 5) to the corresponding magnet on top of the Strap Mate.

HelpWear Inc. (CONFIDENTIAL)

12) Pull the Finger Loop to open the Quick Release (without loosening the Sensor Strap).

[figure not shown]

Figure 6: HeartWatch (top view)

13) Use one hand to secure the strap in place and another to move the Adjustable Sensor along the strap. The Adjustable Sensor typically goes along the Axillary Vein (between the inner bicep and tricep).

14) Once setup has been completed, take the scissor provided and cut the excess fabric on the Disposable Strap with about 0.5 – 1 inch of slack.

COLLECTING DATA

15) Open the HelpWear App and select which HeartWatch unit to pair the smart device to.

[figure not shown]
[figure not shown]

Figure 7: App Screen for Connecting to HeartWatch Devices

Note: Smart Devices with the HelpWear App Installed (and that already paired to the HeartWatch 10) are provided to users for HeartWatch 10.

Note: To connect the HeartWatch 10 to other smart devices, enable the Bluetooth settings of the device and select the HeartWatch 10 to establish the Bluetooth connections. Specific instructions on how to enable Bluetooth settings can be found in the instruction manual of the designated smart device.

16) HeartWatch 10 will assess the placement of the device on the subject. If placement is not correct, the app will guide provide direction on moving the device either left or right or up or down. Once successful, press 'start monitoring' to go into patient mode.

HelpWear Inc. (CONFIDENTIAL)

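### Section 8.11.2 calls the HeartWatch painless and names only minor skin irritation, although the manual in Section 16 foresees strap-related loss of arm circulation

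*Protocol*

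**What the plan says.** Protocol Section 8.11.2 is the section devoted to the risks of the investigational device. It consists of one sentence: "While the HeartWatch is painless and non-invasive, participants may experience minor skin irritation from where it is in contact with their skin". Section 8.11.1, on benefits, also calls the device painless without qualification.

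The Instructions for Use form Section 16 of the same protocol. In step 7 the fitter tightens the strap on the left upper arm. Step 8 then says "Check for signs of loss in circulation in the subject's left arm", and its note explains how this would show: "Loss in circulation can present through the subject feeling numbness, tingling, cold hands, change in skin color, pain, fatigue, or swelling". A remedy follows: "If loss in circulation is detected, repeat step 7", and if the problem persists, consider starting again from step 3 with a larger strap.

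Under Sections 8.0, 9.1, 9.3 and 9.5 the band is worn for as long as the comparator: 72 hours in Arm A and 48 hours in Arm B.

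**The concern.** A risk section should state the effects that the sponsor's own manual foresees. Loss of circulation under a tight strap is a different mechanism from skin irritation, so naming irritation does not cover it. Pain is one of the signs that the manual lists, while 8.11.1 and 8.11.2 call the device painless without any condition on fit.

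The second part concerns timing. The manual places its one scheduled circulation check in the middle of the fitting, and the subject then wears the band for two or three days, largely away from the person who fitted it. Most of the listed signs are ones that the subject would feel first. A subject whose arm becomes numb or swollen during wear should know what it may mean, that the strap can be released, and whom to contact. What is at stake is a small matter of disclosure and subject safety. No estimate or test in the study is affected.

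**Working it through.** No arithmetic beyond counting applies, so the texts are set side by side.

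**1. Risk statement against manual.** The note to step 8 lists seven signs: numbness, tingling, cold hands, change in skin color, pain, fatigue and swelling. Section 8.11.2 names 0 of the 7. Its only named effect is minor skin irritation, which is not on the list.

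**2. Is the effect tied to the device?** Yes. Step 8 directly follows the tightening in step 7, and its remedies are to redo step 7 or use a larger strap. The manual therefore attributes the effect to strap tightness.

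**3. Where the check falls.** Set-up runs from step 1 to step 14. The check is at step 8, so 14 − 8 = 6 set-up steps follow it. Five of them (9 to 13) handle the strap or a sensor:

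- Step 9 pushes down the back hinge: "This secures the strap in place".
- Step 10 has the fitter pull the finger loop "to open the Quick Release in the Sensor Strap and loosen the strap", so that the sensors can be shifted.
- Step 11: "Close the Quick Release by connecting the Magnet Pocket" to its magnet.
- Step 12 opens the quick release again, this time without loosening the strap.
- Step 13 moves the adjustable sensor along the strap: "The Adjustable Sensor typically goes along the Axillary Vein".

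Step 14 trims surplus fabric. None of the six repeats the circulation check. At step 16, during data collection, the app may also direct that the device be moved, again with no check attached.

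**4. Does the check recur later?** Only conditionally. If data quality is inadequate, the manual sends the user back through steps 3 to 11, which include step 8. Its Recommendations say that the device may need tightening but attach no circulation check to that advice. The visible Warnings/Cautions do not mention circulation.

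**5. Other routes by which a problem could be caught during wear.**

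- The manual gives advice on imprints, irritation and dryness, removal steps 19 to 22, and a 24-hour support line.
- Section 10.1 provides instruction on placement, use and troubleshooting.
- Section 10.4 allows unscheduled visits for an adverse event.
- Section 8.12 gives the right to withdraw.

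None of these names the circulation signs or says to loosen the band when they appear.

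**6. Comparison within the protocol.** Section 8.11.3 also calls the comparator recorders painless, but goes on to disclose discomfort from the adhesive electrodes as well as skin irritation. The investigational device has the less complete statement.

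**The case against.** The strongest reply is that nothing here is contradictory. Step 8 describes a fitting error to be corrected at the time, and the word painless describes the band when properly fitted. The hazard, its signs and the remedy already stand in the protocol, because the manual is Section 16 and Section 7.7 points to it. Section 10.5.4 requires staff to review the Instructions for Use, so those fitting the band will have seen step 8. Adverse events are assessed at device return and by telephone 1 to 3 days later (10.2), and an unexpected device result noticed by a participant leads to troubleshooting (7.8). No step after step 8 is described as tightening the strap, and step 10 loosens it. What subjects are told belongs mainly in the consent form, which was not available.

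Much of this stands. The gap is incomplete disclosure; nothing shows that a correctly fitted band hurts. The step order shows only that the final fit is not rechecked, not that it ends up tighter than the fit that was checked. No claim can be made about the consent form.

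The routes cited do not close the gap, however. Staff training informs the fitter, the return visit and telephone call record events after wear has ended, and Section 7.8 concerns device faults. None tells the wearer which signs matter or what to do. That the hazard is described in the manual does not make the one-sentence risk section complete; it shows that the sponsor foresaw an effect which that section omits.

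**Conclusion.** The concern holds as a minor point that should be corrected. Section 8.11.2 omits an effect that the protocol's own attachment foresees, naming 0 of its 7 signs, and uses the word painless without the condition on fit that step 8 implies. The only scheduled check precedes five steps of strap or sensor handling and 72 or 48 hours of wear, and the visible text does not extend the signs to that period.

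No endpoint, sample size or analysis changes. The documents give no rate of circulation signs, so harm cannot be quantified. The conclusion about the wording of 8.11.2 rests on the text alone and is firm. The conclusion that wearers lack an instruction is limited to the visible text: the consent form, or the oral instruction under 10.1, may already supply it.

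**What to change.** - **Section 8.11.2:** make painless conditional on fit, for example by saying that the band is not expected to cause pain when correctly fitted. Add strap compression or loss of circulation in the arm, with the seven signs from the note to step 8. Section 8.11.3 is a model for adding the discomfort after the reassurance. Qualify the same word in 8.11.1.
- **Section 10.1:** add one sentence to the placement and troubleshooting instruction. If any of these signs appears, the subject should loosen the band with the quick release, or remove it, and contact the site.
- **Consent form:** if it already says this, align 8.11.2 and 10.1 with it.

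Adverse-event collection can stay as planned. The cost is one or two sentences in 8.11.2, a matching qualifier in 8.11.1 and one sentence in 10.1, delivered at the existing baseline appointment, with no new visit, form or adverse-event prompt. A subject who loosens or removes the band may lose some HeartWatch recording, which is an acceptable price in a feasibility study.

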8.11.3 Ambulatory ECG Recording Risks

Ambulatory ECGs, Holter and Event Recorder devices are painless and non-invasive. They require the user to keep a log of activities and symptoms, remove and replace skin patches when they are worn for extended periods and carry a monitor (receiver) on their belt or other clothing. Users may experience skin irritation and discomfort from the gel patches (adhesive electrodes) on their skin are required to record the electrical activity of the heart.

8.12 Discontinuation of Study

During study conduct, if the Sponsor or site Principal Investigator discover a condition that indicates that the study should be discontinued, this action will be taken. If the study is terminated, the investigator will inform the ethics board or Institutional Review Board (IRB) of the study termination and the reason(s) for its' termination. If a terminated study is planned to be resumed, the Sponsor may not re-engage without first obtaining ethics approval.

If the study was terminated related to an unanticipated adverse device effect (UADE) the study may not be resumed without IRB and Food and Drug Administration (FDA) approval. If the study was terminated related to withdrawal of IRB approval, the Sponsor shall notify the FDA. The investigator(s) will return all study materials, documentation, and Case Report Forms to the Sponsor. The IRB will be informed of study termination and the reason(s) for the termination by the Sponsor or investigator, as specified by the applicable regulatory requirements.

Conditions that may warrant termination of the study include, but are not limited to, the following:

- Discovery of an unexpected, serious, or unacceptable risk to subjects.

HelpWear Inc. (CONFIDENTIAL)

- Recommendation by an Institutional Review Board or Regulatory authority
- The Sponsor decides to discontinue testing of the study device.

Conditions that may warrant study termination at site include, but are not limited to:

- Failure to comply with pertinent regulations and ethical guidelines
- Deliberate submission of false information
- Inadequate adherence to protocol requirements
- Inadequate enrollment

All subjects have the right to withdraw at any point during the study without prejudice. A subject may be withdrawn from study at any time for any of the following reasons:

- Voluntary withdrawal of consent
- Termination of the study by the Sponsor

The withdrawal of the subject is documented with the case report forms for this study. If a subject withdraws prematurely from the study all documentation must be completed as best as possible up until the withdrawal, such as documenting the patient as "lost". The patient also retains the right to request that any and all data collected up to the point of withdrawal be omitted from the final analysis.

All study-related documents will be stored for 25 years as required for all regulated studies.

A privacy breach is considered unlikely due to the fact that only de-identified data are being collected and provided to the Sponsor. Nonetheless, the Research Ethics Board and the Privacy Office will be notified in the event of a privacy breach.

9.0 ECG Data Collection and Transfer

9.1 Event Recorder

For participants in Arm A, the Event Recorder and HeartWatch will be worn for a period of 72 consecutive hours. The comparator Event Recorder for arm A is the Sirona Event / Holter Recorder (Intricon Datrix Corporation, FDA 510(k) number K112601). Like the HeartWatch, the Sirona records ECG data on demand when the patient has symptoms (manual activation) and has automatic arrhythmia detection for bradycardia, tachycardia, AF, and pauses. It can store up to 2,000 events. Electrodes are placed on the chest and connected, via leads, to the recorder. The Sirona Event Recorder has an input impedance of 5 MΩ, a bandwidth: 0.05 Hz to 40 Hz, samples at 256 samples per second, and has a resolution of 10 bits.

[figure not shown]
Sirona data will be downloaded for analysis with Global ECG Management System (GEMS, CardioComm Inc.) software after the 72 hours, as per usual clinical practice at the participating sites. The GEMS data is stored on the clinic network. As per the usual clinical care pathway, ECG technicians will analyze the Sirona data and the results will be over-read by a cardiologist.

Only the data collected using the Sirona recorders and interpreted using the GEMS software will be used for clinical decision making.

9.2 Event Recorder Event Adjudication

For the purposes of this study in Arm A, at least two cardiac electrophysiologists will adjudicate all clinical events (subject activated episodes, as well as auto-detected abnormal rhythms). Additionally, they will classify these as clinically-interpretable (i.e., adequate quality ECG to make a clinical arrhythmia diagnosis; such as tachycardia, bradycardia, AF event or to exclude a clinical arrhythmia diagnosis). In cases of disagreement between the categorization of initial two cardiac electrophysiologists a third cardiac electrophysiologist will evaluate the data. The final categorization will be based on majority consensus. The categorization of events by the cardiac electrophysiologists will be used as the gold standard by which the HeartWatch is compared.

Event categorizations will be done through a customized research software interface (Figure 2). The interface allowing the HeartWatch and Event Recorder data to be masked (i.e., the data from the devices will appear similar), as will the interpretation of the other cardiac electrophysiologist.

T – Manual Trigger

Figure 2. Customized research software interface.

9.3 Holter Monitor

For participants in Arm B, the Holter and HeartWatch will be worn for a period of 48 consecutive hours. The comparator in Arm B is the SEER Holter recorder (GE Medical Systems Information Technologies, Inc., FDA 510(k) number K130626). The Holter monitor is considered the gold standard for ambulatory ECG recordings. Electrodes are placed on the chest and connected, via leads, to the recorder. Unlike an Event Recorder, the Holter continuously records ECG data. Patients are provided with a diary to record their symptoms and activities. All ECG data, including arrhythmia events, are recorded. The SEER Holter has an input impedance of 10 MΩ, a bandwidth: 0.05 Hz to 40 Hz, samples at 125 samples per second, with a resolution of 10 bits.

HelpWear Inc. (CONFIDENTIAL)

SEER data will be downloaded for analysis with MARS software for analysis after the 48 hours, as per usual clinical practice at the participating sites. The MARS Database is stored on the local clinic network. As per the usual clinical care pathway, ECG technicians will analyze the SEER data and the results will be over-read by a cardiologist.

Only the data collected using the SEER recorders and interpreted using the MARS software will be used for clinical decision making.

9.4 Holter Data Evaluation

For the purposes of this study in Arm AB, the percent of data that is interpretable will be based on hour-by-hour analysis by experienced Holter technicians and confirmed by at least two cardiac electrophysiologists. The over-read adjudications by the cardiac electrophysiologists will be used as the gold standard by which the HeartWatch is compared. Data will be segmented into blocks of one hour. The percentage of data will be calculated as the number of blocks where the overall ECG data is clinically-interpretable (the heart rate is measurable, all bradyarrhythmias and tachyarrhythmias are identified, and abnormal beats are identified) over the total number of blocks recorded (e.g., data interpretable in 17 of 21 blocks = 81%).

9.5 HeartWatch

For participants completing either study, the HeartWatch will be worn for the same length of time as the comparator device. The HeartWatch arm band is designed to provide non-invasive, continuous ECG data. It continuously records ECG data for subsequent, offline analysis using a custom-designed research software product (**Figure 2**). The HeartWatch allows the user to note (flag) symptoms they experience (e.g., palpitations, chest pain, fainting, etc.) to allow for symptom-rhythm correlation and subsequent review by a physician. The HeartWatch displays the elements of an ECG signal to facilitate diagnoses by the physician.

When secured to the left upper arm, the device collects continuous ECG signals from four (4) built-in electrodes and transmits the data to the user's personal communication device (e.g., smartphone) and the cloud using the Android Operating System (OS) and Bluetooth. The HeartWatch is powered by a rechargeable lithium ion battery. The HeartWatch collects a single channel ECG, has bandwidth from 0.67 Hz to 45 Hz (and impedance 10 MΩ), sampling rate of 300 samples per second, and 12-bit resolution.

The data obtained using the HeartWatch and any data analyzed using the customized research software interface will be not used for clinical decision making.

9.6 HeartWatch Data Adjudication

For the purposes of this study in Arm A, at least two cardiac electrophysiologists will adjudicate all clinical events (subject activated episodes, as well as auto-detected abnormal rhythms). Additionally, they will classify these as clinically-interpretable (i.e., adequate quality ECG to make a clinical arrhythmia diagnosis [e.g., tachycardia, bradycardia, or AF event or to exclude a clinical arrhythmia diagnosis]). In cases of disagreement between the categorization of initial two cardiac electrophysiologists a third cardiac electrophysiologist will evaluate the data. The final categorization will be based on majority consensus. The categorization of events by the cardiac electrophysiologists will be used as the gold standard by which the HeartWatch is compared.

HelpWear Inc. (CONFIDENTIAL)

Event categorizations will be done through a customized software interface (**Figure 2**). The interface allowing the HeartWatch and Event Recorder data to be masked (i.e., the data from the devices will appear similar), as will the interpretation of the other cardiac electrophysiologist.

For Arm B, the over-read adjudications of the cardiac electrophysiologists will be used as the gold standard by which the HeartWatch is compared.

10.0 Methods

10.1 Baseline Visit

Unless otherwise specified, the study coordinators will conduct the following study activities.

Prior to collecting ECG data, an assessment of the participant will be conducted to confirm eligibility. Subjects will be provided with the HeartWatch and instructed on proper placement, use, and troubleshooting at the same clinical appointment in which they receive the comparator device. The recorders will be placed and turned on within the same time frame (within 2 hours).

The baseline visit will also include a collection of relevant medical data, including: age, gender, height, weight, blood pressure, medications used, medical history, the indication for the extended ECG test and relevant symptoms.

10.2 Study Visits

Participants will be seen at a baseline visit when they will receive the devices and a subsequent visit where the Event Recorder or Holter monitor data are downloaded and assessment of adverse events conducted. Both of these visits follow the usual clinical work flow and procedures for extended ambulatory ECG testing. Hence, no additional in person study visits, outside of these usual visits will be required. A phone follow-up 1 to 3 days after the ECG monitoring devices are returned will be performed to assess for any adverse events that were not apparent at the time the devices were returned.

10.3 Follow Up

None beyond the stated study periods (72 hours for Arm A and 48 hours for Arm B).

10.4 Unscheduled Visits

There is potential for unscheduled clinic visit occurring in the event of a clinical or study device malfunction, inadequate recording from either device, or the development of an adverse event.

Should clinical or study device malfunction or inadequate recording from either device occur the subject will be offered the opportunity to repeat the recordings. If they chose not to repeat the testing their data will be considered incomplete or they will be excluded from the analyses (see Section 10.2). The details surrounding subject data that is excluded from the analyses (i.e., frequency, device type, device and subject reason(s), and relevant demographic features) will be tabulated and reported.

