8.5 Hypothesis

Paired ECG data from the HeartWatch and comparator devices will be similar in terms of the events documented and the proportion of data that is clinically interpretable.

HelpWear Inc. (CONFIDENTIAL)

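### Section 10.4 gives no rule for keeping or excluding failed recordings whose repeat is declined; where unreadable blocks were recorded, excluding them raises that device's interpretable proportion and distorts the 8.5 comparison

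*Protocol*

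**What the plan says.** Section 10.4 sets the trigger as failure on either side of the pair: "Should clinical or study device malfunction or inadequate recording from either device occur the subject will be offered the opportunity to repeat the recordings". For a subject who declines, it gives two outcomes: "If they chose not to repeat the testing their data will be considered incomplete or they will be excluded from the analyses". It then points to section 10.2. That section covers the baseline and return visits and a phone call, and notes that "no additional in person study visits, outside of these usual visits will be required"; it holds no rule on analysis. Inadequate recording is not defined, and the status of the first recording after a repeat is not stated.

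Section 10.4 does promise a table, by frequency, device type, reasons and demographics, of "The details surrounding subject data that is excluded from the analyses". Section 12.2 separately records device deficiencies.

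The quantity at risk is named in section 8.5, which hypothesises that the paired devices are similar in "the proportion of data that is clinically interpretable". Section 9.4 defines it in one-hour blocks: interpretable blocks "over the total number of blocks recorded". (The text there reads Arm AB; I read it as Arm B.) In Arm A it is a judgement per event: under 9.2 and 9.6 the electrophysiologists adjudicate the events and "they will classify these as clinically-interpretable" or not.

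**The concern.** In a device feasibility study, a malfunction or an unreadable recording is a result. Section 10.4 lets that result stay in the analysis, leave it or be run again, and the choice can be made after the recordings have been seen. If the bad recordings leave, the device that produced them looks better. Because a subject is excluded whichever device failed, the between-device difference also moves, in a direction set by which device failed more.

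The study prepares a larger multi-centre study (8.1, 8.6). Its interpretable proportion is a natural planning input, and 11.3 already works with two such figures: under 10% missing or uninterpretable data expected, and 20% allowed for.

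**Working it through.** **The plan's own figures.** The 9.4 example: 17/21 = 81%. Section 11.3, Arm A: 40 × 0.25 × 3 = 30 events of each type, and 30 × 0.8 = 24. Arm B: 250 h × 0.8 = 200 h. All reproduce.

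**Inputs.** From the documents: 10 Arm B subjects (11.3), 48 h each (9.3), one-hour blocks over recorded blocks (9.4). I apply the 9.4 measure to both devices, as 8.5 implies. Assumed, because the documents give no failure rate: a good recording has 43 of 48 blocks interpretable, a failed one has 10, and failures fall on one device.

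**Case (a): the failing device records all 48 h, much of it unreadable.**

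| Failures | Kept | Excluded | Only a good repeat analysed |
|---|---|---|---|
| 1 of 10 | (9×43 + 10)/480 = 397/480 = 83% | 387/432 = 90% | 430/480 = 90% |
| 2 of 10 | (8×43 + 20)/480 = 364/480 = 76% | 344/384 = 90% | 430/480 = 90% |

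With the wear times of 10.6.1 and two failures: at 36 h (good 32/36) 276/360 = 77% kept, 256/288 = 89% excluded; at 60 h (good 54/60) 452/600 = 75% kept, 432/480 = 90% excluded.

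**Sensitivity.** With f failures in 10, good proportion g and failed proportion q, the rise from exclusion is f(g − q)/10. For f = 1 to 3 and q = 0 to 0.50 it runs from 4 to 27 points at g = 0.90 and from 3 to 24 points at g = 0.80. It is zero when q = g.

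**Between-device difference (HeartWatch minus Holter, 48 h).**
- Two HeartWatch failures, kept: 364/480 − 430/480 = −14 points. After exclusion: 0.
- Two Holter failures, kept: +14 points. After exclusion: 0.
- One failure on each device: 397/480 on both, so 0 kept and 0 after exclusion.

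**Case (b): the failing device stops after 12 h, with 10 of those hours interpretable.** Two failures kept: 364/(384 + 24) = 364/408 = 89.2%. Excluded: 344/384 = 89.6%. The choice hardly matters. But only 408/480 = 85% of planned hours were recorded, and the 9.4 proportion does not show it. In between, if the 12 recorded blocks are themselves poor (25%, others at 90%), the result is (345.6 + 6)/408 = 86.2% kept and 90.0% excluded.

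**The 200 h criterion (11.2).** At 48 h per subject, excluding two leaves 344 interpretable hours on the device that failed. At the 250 h of 11.3 (25 h per subject), it leaves 8 × 25 = 200 h recorded and 200 × 43/48 = about 179 h interpretable. Whether the criterion survives exclusions therefore depends on the hours per subject.

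**The case against.** The strongest reply is that little rides on this. The proportion is not an endpoint listed in 8.7 or a count in 11.2, 11.1 calls the objectives largely logistical, and 11.4 plans descriptive statistics. That stands, and it limits the consequence to an estimate and the 8.5 comparison.

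Second, which recording is analysed could be left to a separate analysis plan, and the two outcomes might simply mean partial data kept versus no usable data. In part this stands: the documents may intend that. But the protocol itself names exclusion as an outcome of device failure and points to a section without a rule, so it has fixed the matter badly rather than left it open.

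Third, disclosure is largely in place through the 10.4 table and the deficiency form of 12.2. This too stands in part. Disclosure does not correct the proportion, and a failed first attempt that is then repeated need not appear in the 10.4 table.

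Fourth, two failures kept give 24% uninterpretable, above the 20% that 11.3 calls conservative. True; one failure (17%) lies within it and still moves the figure by 7 points.

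Stronger readings are tempting but not supported:
- That exclusion always raises the proportion. It does so only when recorded blocks are worse than the rest.
- That 10.4 makes a repeat overwrite the first recording. It is silent on this.
- That the rule favours the HeartWatch. The trigger is failure of either device.
- That exclusion inflates the 20/20/200 h counts. It can only lower them; repeats can raise them.

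**Conclusion.** The concern holds in a limited form. Section 10.4 permits exclusion because of device failure without a rule, its cross-reference leads nowhere, and it leaves the status of a repeated recording open. When failed recordings contain recorded but unreadable blocks, excluding them or analysing only the repeat raises that device's proportion: by about 7 points for one failure in 10 and 14 for two, under the assumed rates. When a device stops early the choice matters little, and the weakness is instead that the 9.4 denominator omits the lost hours.

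The sizes are illustrations. Arm A is not quantified: 11.3 expects events in only about 25% of patients, so excluding a subject without events leaves an event-based proportion unchanged. No formal test is affected. The protocol should be corrected, because the change is cheap and the proportion is what 8.5 compares.

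**What to change.** In section 10.4, replace the two alternatives with one rule:
- The first recording of every subject fitted with both devices stays in the interpretable-proportion analysis. The exception is a withdrawing subject's request under 8.12 that "any and all data collected up to the point of withdrawal be omitted from the final analysis".
- Recorded unreadable blocks (Arm B) or captured unreadable events (Arm A) count as not interpretable for that device only.
- Hours never recorded are handled separately. Keep the 9.4 proportion over recorded blocks and report beside it, per device, hours recorded out of hours planned. This first needs the Arm B wear times to be reconciled: 48 h in 9.3, up to 48 h in 8.0, and 36 to 60 h in 10.6.1.
- Repeat recordings are reported separately. They may still count towards the 20/20/200 h criteria, with the share from repeats shown.
- The 10.4 table is extended to failed first attempts that were repeated.
- Inadequate recording is defined, and the reference to 10.2 is corrected.

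The cost is protocol wording and one extra table, with no new data. The reported yield may be lower.
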